## 6.2 Other Agent(s)

*Dose modification guidelines for talimogene laherparepvec are listed in Section 6.1.*

Event Name	Oxaliplatin Neuropathy		
	Duration of Toxicity		
Grade of Event	1-7 days	>7 days	Persistent between cycles
Grade 1 Paresthesias/dysesthesias b that do not interfere with function	No change in dose	No change in dose	No change
Grade 2 Paresthesias/dysesthesias b interfering with function, but not activities of daily living (ADL)	No change in dose	No change in dose	Decrease by 1 dose level
Grade 3 Paresthesias/dysesthesias b with pain or with functional impairment that also interfere with ADL	No change	Decrease by 1 dose level	Stop oxaliplatin
Grade 4 Persistent paresthesias/dysesthesias that are disabling or life- threatening	Stop oxaliplatin	Stop oxaliplatin	Stop oxaliplatin
Laryngopharyngeal dysesthesia	↑ duration of next infusion to 6 hours c		

a Not resolved by the beginning of the next cycle.

b May be cold induced.

Event Name	Oxaliplatin hypersensitivity
Grade of Event	Management/Next Dose for Oxaliplatin
≤ Grade 1	Premedications with antihistamines, steroids and slow rate of oxaliplatin by half with future doses
Grade 2	Premedications with antihistamines, steroids and slow rate of oxaliplatin by half with future doses or discontinue oxaliplatin per discretion of treating physician
Grade 3	Discontinue oxaliplatin
Grade 4	Discontinue oxaliplatin
*Patients requiring a delay of >2 weeks should go off protocol therapy.	

Event Name	Hand Foot Syndrome	
	Management/Next Dose for Oxaliplatin	Management/Next Dose for 5-FU
≤ Grade 1	No change in dose	No change in dose
Grade 2	No change in dose	No change in dose
Grade 3	Hold all treatment until recovery ≤ grade 1 but may continue radiation if deemed safe by investigators; No change in dose	Hold all treatment until recovery ≤ grade 1 but may continue radiation if deemed safe by investigators; No change in dose
Grade 4	Off protocol therapy	Off protocol therapy
*Patients requiring a delay of >2 weeks should go off protocol therapy.		

Event Name	Vomiting	
	Management/Next Dose for Oxaliplatin	Management/Next Dose for 5-FU
≤ Grade 1	No change in dose	No change in dose
Grade 2	Hold until ≤ Grade 1. Resume at same dose level.	Hold until ≤ Grade 1. Resume at same dose level.
Grade 3	Hold* until < Grade 2. Resume at one dose level lower, if indicated.	Hold* until < Grade 2. Resume at one dose level lower, if indicated. **

Grade 4	Off protocol therapy	Off protocol therapy
*Patients requiring a delay of >2 weeks should go off protocol therapy.		
Recommended management: ondansetron 4-8 mg ODT or by mouth every 6-8 hours and / or prochlorperazine 5-10 mg po every 4-6 hours or other anti-emetics per treating physician		

Event Name	Diarrhea	
	Management/Next Dose for Oxaliplatin	Management/Next Dose for 5-FU
≤ Grade 1	No change in dose	No change in dose
Grade 2	No change in dose	No change in dose
Recurrent / persistent grade 2	Decrease by 1 dose level	Decrease by 1 dose level
Grade 3	Hold* until < Grade 2. Resume at one dose level lower, if indicated.	Hold* until < Grade 2. Resume at one dose level lower, if indicated. **
Grade 4	Off protocol therapy	Off protocol therapy
*Patients requiring a delay of >2 weeks should go off protocol therapy.		
Recommended management: Loperamide antidiarrheal therapy Dosage schedule: 4 mg at first onset, followed by 2 mg with each loose motion until diarrhea-free for 12 hours (maximum dosage: 16 mg/24 hours) Adjunct anti-diarrheal therapy is permitted and should be recorded when used.		

Event Name	Neutropenia	
	Management/Next Dose for Oxaliplatin	Management/Next Dose for 5-FU
≤ Grade 1	No change in dose	No change in dose
Grade 2	Hold until ≤ Grade 1. Resume at same dose level; consider growth factor with next cycle	Hold until ≤ Grade 1. Resume at same dose level; consider growth factor with next cycle.
Grade 3	Hold* until < Grade 2. Resume at one dose level lower, if indicated; consider growth factor with next cycle especially if dose reduction not done.	Hold* until < Grade 2. Resume at one dose level lower, if indicated; consider growth factor with next cycle especially if dose reduction not done.
Grade 4	Off protocol therapy	Off protocol therapy
*Patients requiring a delay of >2 weeks should go off protocol therapy.		
Consider GM-CSF per recommended doses		

Event Name	Thrombocytopenia
------------	------------------

Grade of Event	Management/Next Dose for [Agent Name]	Management/Next Dose for [Agent Name]
≤ Grade 1	No change in dose	No change in dose
Grade 2	Hold until ≤ Grade 1. Resume at same dose level.	Hold until ≤ Grade 1. Resume at same dose level.
Recurrent Grade 2	Hold until ≤ Grade 1. Decrease by one dose level	Hold until ≤ Grade 1. Decrease by one dose level
Grade 3	Hold* until < Grade 2. Resume at one dose level lower	Hold* until < Grade 2. Resume at one dose level lower
Grade 4	Off protocol therapy	Off protocol therapy

\*Patients requiring a delay of >2 weeks should go off protocol therapy.

Event Name	Mucositis	
Grade of Event	Oxaliplatin	5-FU
≤ Grade 1 or grade 2 but tolerable to patient	No change in dose	No change in dose
Grade 2 but intolerable to patient	No change in dose	Decrease by one dose level
Grade 3	Hold all treatment until < Grade 2. No change in dose	Hold all treatment until < Grade 2. Decrease by one dose level
Grade 4	Discontinue treatment	Discontinue treatment

\* Patients requiring a delay of >2 weeks should go off protocol therapy.

Recommended Management: Oral hygiene, topical mucosal coating agents such as diphenhydramine, compounded mixtures of topical anaesthetics

Event Name	Fatigue	
Grade of Event	Oxaliplatin	5-FU
≤ Grade 1 or grade 2 but tolerable to patient	No change in dose	No change in dose
Grade 2 but intolerable to patient	Decrease by one dose level	Decrease by one dose level
Grade 3	Hold all treatment until < Grade 2. Decrease by one dose level	Hold all treatment until < Grade 2. Decrease by one dose level
Grade 4	Discontinue treatment	Discontinue treatment

\* Patients requiring a delay of >2 weeks should go off protocol therapy.

Recommended Management: Physical exercise / therapy, light exposure, evaluate for contributing factors including medications, anemia, poor sleep hygiene

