### 1.3 Exploratory Objectives

- 1.3.1 To correlate genomic information including RAS, RAF mutation status with response, DFS and / or OS.
- 1.3.2 To determine immunodulatory changes following talimogene laherparepvec, chemotherapy and radiation treatment including proportions of immune cell infiltrates in serially collected peripheral blood and/or frozen tumor samples (pre-, on treatment, and at post progression)
- 1.3.3 To identify MRI-based features including mrCRM at baseline or post-therapy mrCRM, mrTRG to define determinants of response, DFS and OS
- 1.3.4 To determine the disease free survival (DFS) and overall survival (OS) of talimogene laherparepvec with chemotherapy and radiation in patients undergoing curative resection
- 1.3.5 To determine the pathological complete response (pCR) rate of talimogene laherparepvec with chemotherapy and radiation

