## 2.2 CTEP IND Agents

### 2.2.1 Talimogene laherparepvec (talimogene laherparepvec)

Talimogene laherparepvec is an attenuated herpes simplex virus type 1 (HSV-1) [REDACTED]

[REDACTED] M-CSF recruits and activates antigen presenting cells which can process and present tumor-derived antigens to promote an effector T-cell response.

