**Antitumor Activity:**

Talimogene laherparepvec demonstrated initial biological activity as monotherapy in subjects with advanced solid tumors with metastases in the skin or subcutaneous (SC) tissue as evidenced by necrosis or apoptosis in tumor biopsies (Study 001/01).

In a phase III trial in melanoma (Study 005/05 “A Randomized Phase 3 Clinical Trial to Evaluate the Efficacy and Safety of treatment with OncoVEXGM-CSF Compared to Subcutaneously Administered GM-CSF in Melanoma Patients with Unresectable Stage IIIb, IIIc and IV Disease”), talimogene laherparepvec demonstrated an improvement in the primary endpoint, durable response rate (DRR) (defined as complete response [CR] or partial response [PR] maintained for  $\geq$  6 months continuously and which had its onset on the first 12 months of treatment): 16.3% vs. 2.1%. Overall survival (OS) was a secondary endpoint. At the primary analysis, median OS was 23.3 (95% confidence interval [CI]: 19.5, 29.6) months in the talimogene laherparepvec arm and 18.9 (95% CI: 16.0, 23.7) months in the GM-CSF arm (hazard ratio [HR] 0.79; 95% CI: 0.62, 1.00;  $p = 0.051$ ). At final analysis, with an additional follow-up of 5 months (median 49 months [range, 37-63]), median OS remained 4.4 months longer for talimogene laherparepvec compared with GM-CSF (23.3 vs 18.9 months; HR 0.79, 95% CI: 0.62-1.00,  $P = 0.0494$ , descriptive). Results from the phase 2 study in melanoma (002/03) also support the efficacy of talimogene laherparepvec for the treatment of melanoma.

Response to talimogene laherparepvec can be delayed, and the phenomenon sometimes referred to as “pseudoprogression” has been observed. In the pivotal clinical trial, the median time to response onset was 4.1 months (ranged from 1.2 to 16.7 months).

Approximately 50% of the patients ultimately achieved a response had evidence of increase in the size of existing lesions and/or development of new lesions.

Pseudoprogression can also be seen with other immunotherapies. Patients may continue treatment if there was increase in the size of existing lesions or development of new lesions, as long as the investigator determined that initiation of a new treatment was not required.

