Talimogene laherparepvec infection of tumor or non-tumor tissues could potentially lead to establishment of latency and subsequent reactions of talimogene laherparepvec if the virus comes into contact with axonal nerve terminals and was transported to neuronal cell bodies. In mice, biodistribution studies have detected low levels of talimogene laherparepvec in trigeminal ganglia through 28 days in 1 of 6 animals following high-dose IV administration ( $0.6 \times 10^7$  PFU, ~36-fold over the highest proposed clinical dose). Talimogene laherparepvec was undetectable in trigeminal ganglia in mice after subcutaneous administration.

- 4) Recombination of talimogene laherparepvec with wild-type HSV-1: This event has not been reported in the phase 3 melanoma clinical study. The genetic modifications made to talimogene laherparepvec only attenuate the virus, either by limiting replication to tumor cells and neurovirulence (by deletion of ICP34.5) or enhancing immune detection of infected cells (by eliminating ICP47), none of the theoretical products of recombination between wild-type HSV-1 and talimogene laherparepvec would have increased virulence. The likelihood of recombination occurring is low, and if recombination occurred, the virulence of the recombinants would be no greater than wild-type HSV-1, and symptoms will be reduced compared to wild-type HSV-1. Management with systemic antivirals would be the same.
- 5) Talimogene laherparepvec-mediated anti-GM-CSF antibody response: There is a theoretical concern that transgene-derived expression of GM-CSF could induce an immune response reactive with endogenous GM-CSF. Autoantibodies against GM-CSF is detected in 9.6% general population. It is not known whether such phenomena could be expected with the limited exposure anticipated with transgene expression of GM-CSF from talimogene laherparepvec.

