#### 2.6.4.3 Hypothesis

We hypothesize that the local and systemic immune effects of talimogene laherparepvec may cooperate with neoadjuvant therapy to increase locoregional control in rectal cancer. We propose to quantify changes in a) tumor immune cell infiltration and to characterize subtypes of the immune cells by IHC b) peripheral T cell subpopulations by flow cytometry with talimogene laherparepvec injection and radiation in rectal cancer.

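### The neutropenia table names GM-CSF, the study virus's own transgene product, as its only growth factor; given with an early FOLFOX cycle, it adds a second source of that cytokine before the on-treatment immune samples

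*Combined protocol and SAP*

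**What the plan says.** **Growth factor.** In the Section 6.2 neutropenia table, the grade 2 row holds FOLFOX until recovery and then says "Resume at same dose level; consider growth factor with next cycle". The grade 3 row gives similar advice, with a dose reduction if indicated. Neither row names a product. The footer does: "Consider GM-CSF per recommended doses". No other growth factor is named in the readable text. Grade 4 leaves protocol therapy, and for long holds "Patients requiring a delay of >2 weeks should go off protocol therapy".

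**GM-CSF and the virus.** Section 2.2.1.2.2 discusses "transgene expression of GM-CSF from talimogene laherparepvec". Section 2.2.1 is partly blacked out and the start of the cytokine's name is cut, but the text that remains says it "recruits and activates antigen presenting cells which can process and present tumor-derived antigens to promote an effector T-cell response". In the pivotal melanoma trial described in Section 2.2.1.1, the virus was "Compared to Subcutaneously Administered GM-CSF in Melanoma Patients", so GM-CSF was the control treatment.

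**Readouts.** Exploratory objective 1.3.2 concerns "proportions of immune cell infiltrates in serially collected peripheral blood and/or frozen tumor samples" after virus, chemotherapy and radiation. Section 2.6.4.3 plans to quantify "peripheral T cell subpopulations by flow cytometry with talimogene laherparepvec injection and radiation in rectal cancer". Section 9.9.5 assigns lymphocyte subsets in tumour and blood to flow cytometry. Section 2.6.5.3 hypothesises that tumour GM-CSF by immunohistochemistry will be one sign of successful viral delivery.

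**Handling.** Section 5.4 restricts anti-herpetic drugs only. Section 13.4 reports the correlative studies descriptively and has no rule for growth-factor use. The Section 10 calendar collects concurrent medication.

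**The concern.** Most supportive drugs are incidental to what an oncolytic virus does. This one is not: it is the virus's payload, and the protocol credits that payload with recruiting antigen-presenting cells and driving a T-cell response. A patient given systemic GM-CSF before the on-treatment sample has a second source of the cytokine, so that patient's immune-cell change cannot be read as following study treatment alone. The delivery hypothesis has the same weakness, because GM-CSF is itself one of its proposed markers.

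At stake is the interpretation of a small set of exploratory summaries that may inform later work. No dose decision depends on them.

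**Working it through.** The plan gives no figure to reproduce. The check sets the schedule beside the sampling times.

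1. **Trigger.** Grade 2 or 3 neutropenia, with growth factor considered at the next cycle (Section 6.2).

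2. **Cycles before sampling.** Under Section 5.1, FOLFOX is given at weeks 1, 3, 5 and 7, and virus at weeks 0, 3, 5 and 7. Neutropenia after the week 1 or week 3 cycle can lead to growth factor at week 3 or week 5, while virus dosing is under way.

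3. **Sampling.** The specimen table in Section 9.1 puts on-treatment tissue and sodium-heparin blood at week 7. Section 9.2.3 puts the sodium-heparin draw at week 8. Section 9.1 links that tube to flow cytometry, so both times are carried forward.

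4. **Interval from growth factor to sample, with no hold.**
   - Given at week 3: 7 − 3 = 4 weeks, or 8 − 3 = 5 weeks.
   - Given at week 5: 7 − 5 = 2 weeks, or 8 − 5 = 3 weeks.

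   Exposure comes before the sample in all four cases. With holds of up to 2 weeks the interval changes. For example, neutropenia found at week 3 and held for 2 weeks puts the resumed cycle at week 5, still 2 or 3 weeks before sampling if the sample keeps its calendar week. I give no count of affected cycles, because it depends on the length of the hold, on whether the next cycle means the resumed one or the one after it, and on week 7 versus week 8.

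5. **How many patients.** This is not derivable. Section 2.3.1 reports neutropenia in 73% of patients on oxaliplatin with 5-FU and leucovorin (44% grade 3 or 4). That shows the trigger is common, but these are not rates by week 7, and they say nothing about GM-CSF use. Purely as an assumption, let each of the 15 patients at the MTD (Section 13.1) have chance p of receiving GM-CSF before the sample. The expected number exposed is 15p, and the chance of at least one is 1 − (1 − p)^15:

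| Assumed p | Expected exposed | Chance of at least one |
|---|---|---|
| 5% | 0.75 | 54% |
| 10% | 1.5 | 79% |
| 20% | 3.0 | 96% |

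6. **Weight of one sample.** 1/15 = 6.7% of a 15-patient summary. The share is larger if fewer patients contribute, and note i in Section 10 makes biopsies optional. This is a weight in the summary and does not measure bias.

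7. **Safeguards.** Neither Section 5.4 nor Section 13.4 separates exposed samples. The removed and blacked-out parts of Section 9 cannot be checked.

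**The case against.** The strongest reply has four parts.

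**Nothing requires GM-CSF.** The rows allow any growth factor, and the footer only asks the clinician to consider GM-CSF. A reader might infer that the protocol mandates it or rules out alternatives; the text does neither. The footer may even be a slip for G-CSF, which the documents cannot settle. This limits how often the problem would arise. Still, GM-CSF is the only product named, and the correction is the same if it is a slip.

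**Absence cannot be proved.** A reader might infer that the plan nowhere deals with growth-factor exposure. That goes too far: parts of Section 9, where the assay plan would sit, are removed or blacked out. The claim covers the readable text only.

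**Any added drug affects the readout.** Steroid premedication for oxaliplatin hypersensitivity is one example, and the documents do not show that G-CSF would leave lymphocyte subsets unchanged. That is fair, and naming G-CSF does not make the samples clean. GM-CSF differs because it duplicates the agent's payload and one of its proposed delivery markers.

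**The data are already collected.** Concurrent medication is on the calendar, so exposed samples can be identified later. This stands, and it is why the analysis part of the fix is optional. With so few samples, a rule set in advance is still better than choosing afterwards which to set aside.

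**Conclusion.** The point holds as a minor one. The only growth factor named is the virus's transgene product, and the schedule allows it before the on-treatment immune samples. An exposed sample then has a second source of the cytokine, which no readable rule separates out.

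This rests on three assumptions: that some clinicians follow the footer, that samples are taken at about week 7 or 8, and that the cytokine with the cut name in Section 2.2.1 is GM-CSF, as Section 2.2.1.2.2 indicates. The immunohistochemistry marker is affected only if that assay is run; in the readable text it appears only as a background hypothesis. The number affected and the size and direction of any effect remain unknown.

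A reader might go further and infer that the trial's main conclusions are at risk. The documents do not support that. The affected readouts are exploratory and descriptive, and the primary endpoint, DLT rule, MTD, neoadjuvant rectal score and sample size do not use them.

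**What to change.** In the footer of the Section 6.2 neutropenia table, replace GM-CSF with a growth factor that is not the transgene product, for example G-CSF. Do not bar GM-CSF; clinicians keep their choice.

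Optionally, add one sentence to Section 13.4: samples taken after systemic GM-CSF will be flagged from the concurrent-medication record, and the descriptive immune-cell summaries (and GM-CSF immunohistochemistry, if run) will be reported with and without them.

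The cost is one word and, if adopted, one sentence. No new data field is needed and growth-factor support is unchanged. The downside is that GM-CSF is no longer the named default, and a few exploratory samples may drop out of one version of a summary.

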## 7. ADVERSE EVENTS: LIST AND REPORTING REQUIREMENTS

Adverse event (AE) monitoring and reporting is a routine part of every clinical trial. The following list of AEs (Section 7.1) and the characteristics of an observed AE (Sections 7.2 and 7.3) will determine whether the event requires expedited reporting via the CTEP Adverse Event Reporting System (CTEP-AERS) in addition to routine reporting

### 7.1 Comprehensive Adverse Events and Potential Risks List(s) (CAEPRs)

The Comprehensive Adverse Event and Potential Risks list (CAEPR) provides a single list of reported and/or potential adverse events (AE) associated with an agent using a uniform presentation of events by body system. In addition to the comprehensive list, a subset of AEs, the Specific Protocol Exceptions to Expedited Reporting (SPEER), appears in a separate column and is identified with **bold** and *italicized* text. The SPEER is a list of events that are protocol-specific exceptions to expedited reporting to NCI (except as noted below). Refer to the 'CTEP, NCI Guidelines: Adverse Event Reporting Requirements'

[http://ctep.cancer.gov/protocolDevelopment/adverse\\_effects.htm](http://ctep.cancer.gov/protocolDevelopment/adverse_effects.htm) for further clarification.

The CAEPR may not provide frequency data; if not, refer to the Investigator's Brochure for this information.

**NOTE:** The highest grade currently reported is noted in parentheses next to the AE in the SPEER. Report **ONLY** AEs higher than this grade expeditiously. If this CAEPR is part of a combination protocol using multiple investigational agents and has an AE listed on different SPEERs, use the lower of the grades to determine if expedited reporting is required.

#### 7.1.1 CAEPRs for CTEP IND Agent(s)

##### 7.1.1.1 CAEPR for talimogene laherparepvec

**Comprehensive Adverse Events and Potential Risks list (CAEPR)**  
**for**  
**Talimogene Laherparepvec(NSC 785349)**

**Comprehensive Adverse Events and Potential Risks list (CAEPR)**  
**for**  
**Talimogene Laherparepvec (T-VEC, IMLYVIC, NSC 785349)**

The Comprehensive Adverse Events and Potential Risks list (CAEPR) provides a single list of reported and/or potential adverse events (AE) associated with an agent using a uniform presentation of events by body system. In addition to the comprehensive list, a subset, the Specific Protocol Exceptions to Expedited Reporting (SPEER), appears in a separate column and is identified with bold and italicized text. This subset of AEs (SPEER) is a list of events that are protocol specific exceptions to expedited reporting to NCI (except as noted below). Refer to the 'CTEP, NCI Guidelines: Adverse Event Reporting Requirements' [http://ctep.cancer.gov/protocolDevelopment/electronic\\_applications/docs/aeguidelines.pdf](http://ctep.cancer.gov/protocolDevelopment/electronic_applications/docs/aeguidelines.pdf) for further clarification. *Frequency is provided based on 517 patients.* Below is the CAEPR for Talimogene

laherparepvec (T-VEC, IMLYGIC).

**NOTE:** Report AEs on the SPEER **ONLY IF** they exceed the grade noted in parentheses next to the AE in the SPEER. If this CAEPR is part of a combination protocol using multiple investigational agents and has an AE listed on different SPEERs, use the lower of the grades to determine if expedited reporting is required.

Version 2.1, August 22, 2017

Adverse Events with Possible Relationship to Talimogene laherparepvec (T-VEC, IMLYGIC) (CTCAE 5.0 Term) [n= 517]			Specific Protocol Exceptions to Expedited Reporting (SPEER)
Likely (>20%)	Less Likely (<=20%)	Rare but Serious (<3%)	
BLOOD AND LYMPHATIC SYSTEM DISORDERS	Anemia		Anemia (Gr 2)
GASTROINTESTINAL DISORDERS	Abdominal pain		Abdominal pain (Gr 2)
	Constipation		Constipation (Gr 2)
	Diarrhea		Diarrhea (Gr 2)
Nausea			Nausea (Gr 2)
Vomiting			Vomiting (Gr 2)
GENERAL DISORDERS AND ADMINISTRATION SITE CONDITIONS			
Chills			Chills (Gr 2)
Fatigue			Fatigue (Gr 2)
Fever			Fever (Gr 2)
Flu like symptoms			Flu like symptoms (Gr 2)
Injection site reaction 			Injection site reaction  (Gr 2)
	Pain 		Pain  (Gr 2)
IMMUNE SYSTEM DISORDERS		Autoimmune disorder 	
INFECTIONS AND INFESTATIONS			
	Infections and infestations - Other (herpetic keratitis)		
	Infections and infestations - Other (oral herpes)		
	Skin infection 		Skin infection  (Gr 2)
INJURY, POISONING AND PROCEDURAL COMPLICATIONS			
	Wound complication 		
INVESTIGATIONS			
	Weight loss		Weight loss (Gr 2)
METABOLISM AND NUTRITION DISORDERS			
	Anorexia		
	Dehydration		
MUSCULOSKELETAL AND CONNECTIVE TISSUE DISORDERS			
	Arthralgia		Arthralgia (Gr 2)
	Myalgia		Myalgia (Gr 2)
	Pain in extremity		Pain in extremity (Gr 2)
NEOPLASMS BENIGN, MALIGNANT AND UNSPECIFIED (INCL CYSTS AND POLYPS)			

Adverse Events with Possible Relationship to Talimogene Laherparepvec (T-VEC, IMLYVIC) (CTCAE 5.0 Term) [n= 517]			Specific Protocol Exceptions to Expedited Reporting (SPEER)
Likely (>20%)	Less Likely (<=20%)	Rare but Serious (<3%)	
		Neoplasms benign, malignant and unspecified (incl cysts and polyps) - Other (plasmacytoma at the injection sites)	
NERVOUS SYSTEM DISORDERS			
	Dizziness		
	Headache		Headache (Gr 2)
RESPIRATORY, THORACIC AND MEDIASTINAL DISORDERS			
	Pharyngolaryngeal pain		Pharyngolaryngeal pain (Gr 2)
		Respiratory, thoracic and mediastinal disorders - Other (obstructive airway disorder) 	
SKIN AND SUBCUTANEOUS TISSUE DISORDERS			
	Pruritus		
	Rash 		
	Skin and subcutaneous tissue disorders - Other (dermatitis)		
	Skin and subcutaneous tissue disorders - Other (vitiligo) 		
VASCULAR DISORDERS			
	Flushing		
	Thromboembolic event (venous)		
		Vascular disorders - Other (carotid artery blowout syndrome) 	

This table will be updated as the toxicity profile of the agent is revised. Updates will be distributed to all Principal Investigators at the time of revision. The current version can be obtained by contacting [[contact]](mailto:[contact]). Your name, the name of the investigator, the protocol and the agent should be included in the e-mail.

Injection site reactions may include redness, swelling, and bleeding.

Pain can occur in the tumor, injection sites and nodal draining (axilla and groin etc) lymph nodes.

Several events which are autoimmune-mediated, such as acute kidney injury (acute renal failure), glomerulonephritis (nephritis), worsening of psoriasis, pneumonitis, vasculitis, and vitiligo (areas of skin with loss of color) have been observed in clinical trials of talimogene laherparepvec.

Skin infection (cellulitis) can be complicated with local and systemic infection, tissue necrosis, and ulceration, or wound complications.

Wound complication may occur at the injection site and may include wound infection and poor healing.

Obstructive airway disorder has occurred in one patient with Head and Neck Squamous cell carcinoma (HNSCC) with a supraventricular mass who developed acute respiratory distress requiring a tracheotomy 13 days after the second dose of T-VEC. Imaging showed a mass in the larynx and adjacent lymph nodes on the contralateral side.

Rash may include rash maculo-papular and erythematous rash.

Carotid artery blowout syndrome was observed in a HNSCC patient treated with T-VEC in combination with anti-PD-1 who had been previously treated with localized (neck) radiation and lymph node dissection.

**Adverse events reported on talimogene laherparepvec (T-VEC, IMLYGIC) trials, but for which there is insufficient evidence to suggest that there was a reasonable possibility that talimogene laherparepvec (T-VEC, IMLYGIC) caused the adverse event:**

**BLOOD AND LYMPHATIC SYSTEM DISORDERS** - Febrile neutropenia

**CARDIAC DISORDERS** - Sinus tachycardia

**EAR AND LABYRINTH DISORDERS** - Tinnitus

**GASTROINTESTINAL DISORDERS** - Ascites; Dry mouth; Dysphagia; Gastrointestinal disorders - Other (odynophagia); Mucositis oral

**GENERAL DISORDERS AND ADMINISTRATION SITE CONDITIONS** - Edema limbs; Malaise

**INFECTIONS AND INFESTATIONS** - Infections and infestations - Other (oral candidiasis)

**INJURY, POISONING AND PROCEDURAL COMPLICATIONS** - Bruising; Dermatitis radiation; Fracture

**INVESTIGATIONS** - Neutrophil count decreased; White blood cell decreased

**METABOLISM AND NUTRITION DISORDERS** - Hypokalemia

**NERVOUS SYSTEM DISORDERS** - Cognitive disturbance; Dysgeusia

**PSYCHIATRIC DISORDERS** - Anxiety; Confusion; Insomnia

**RESPIRATORY, THORACIC AND MEDIASTINAL DISORDERS** - Dyspnea; Pneumonitis

**Note:** Talimogene laherparepvec (T-VEC, IMLYGIC) in combination with other agents could cause an exacerbation of any adverse event currently known to be caused by the other agent, or the combination may result in events never previously associated with either agent.

**Note:** In animal models talimogene laherparepvec has demonstrated several potential risks as detailed below:

- 1) Talimogene laherparepvec has not been tested in severely immune compromised patients. In animal models, injection of talimogene laherparepvec in immune-deficient mice resulted in disseminated infection.
- 2) Transmission of talimogene laherparepvec to health care professionals and personnel in close contact is possible.
- 3) Latent infection of talimogene laherparepvec in the neurological system has been observed in mice at high dose of T-VEC, although the clinical implication in human patients is not clear.

